#### 9.3.3.2.2. Statistical Analysis of the Secondary PK Endpoints during Exercise

A mixed-effects model without log transformation that includes treatment (Lyumjev, Humalog), sequence, period, and treatment as fixed effects and subject as a random effect may be used for the exploratory PK endpoints during the exercise period. LSmeans, treatment differences in LSmeans, and the corresponding 90% CIs for the treatment differences will be estimated from the model. The p-value on the difference between LSmeans will be used to determine statistical significance. The treatment ratios and 90% CIs for the ratios will be calculated using the Fieller's theorem (Chow and Liu 2009).

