4.2 Secondary Objectives and Endpoints

The secondary objectives of the study are:

- To compare the glucodynamic response with Lyumjev versus Humalog during a dinner mixed-meal tolerance test (MMTT) following moderate-intensity aerobic exercise using either 50% or 100% reduction of basal infusion rates, set 60 minutes or 15 minutes before the onset of exercise, respectively
- To compare the PK of insulin lispro between Lyumjev versus Humalog during an MMTT
- To compare the PK of insulin lispro between Lyumjev versus Humalog during 60 minutes of moderate-intensity aerobic exercise using either 50% or 100% reduction of basal infusion rates with Lyumjev or Humalog, set 60 minutes or 15 minutes before the onset of exercise, respectively.

The secondary endpoints of the study are:

- Postprandial PG excursion during the test meal (e.g., area under the plasma concentration versus time curve [AUC] from time 0 to 4 hours [AUC{0-4h}])
- Insulin lispro PK during the MMTT after exercise
- Insulin lispro PK during the exercise.

4.3 **Exploratory Objectives and Endpoints**

The exploratory objectives of the study are:

- To investigate tolerability and safety of Lyumjev and/or Humalog
- To perform an exploratory comparison of glucose variability, time in range, hypoglycemia, and hyperglycemia using continuous glucose monitoring (CGM) profiles obtained from participants receiving Lyumjev and Humalog.

The exploratory endpoints of the study are:

- Incidence of treatment-emergent adverse events (TEAEs), serious adverse events (SAEs), symptomatic hypoglycemia
- Blood ketone levels
- Overall variability (coefficient of variation [CV] and standard deviation [SD])
- Time in range (70 to 180 mg/dL) during exercise, MMTT assessment, overnight period, and for the entire in-house period
- Time in hypoglycemia (<70 and <54 mg/dL) and hyperglycemia (>180 and 140 mg/dL)
- Mean glucose levels.

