7. SAMPLE SIZE JUSTIFICATION

Approximately 32 participants may be enrolled to ensure that at least 28 participants complete the study.

This sample size will provide approximately 80% power to demonstrate a 14-mg/dL difference in the change in PG level from start to the end of the exercise between Lyumjev and Humalog, assuming no true difference in the change in PG level between Lyumjev and Humalog and a SD of 27.9 mg/dL with a 2-sided alpha-level of 0.1. Discontinued participants may be replaced to ensure that 28 participants complete the trial. A replacement participant will be assigned to the same treatment sequence as the participant being replaced.

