9. STATISTICAL METHODOLOGY

9.1 General

Data listings will be provided for all data that is databased. Summary statistics and statistical analysis will only be presented for data where detailed in this SAP. For continuous data, summary statistics will include the arithmetic mean, arithmetic SD, median, min, max and n; for log-normal data (e.g. the PK parameters: AUCs and maximum observed drug concentration [C_{max}]) the geometric mean and geometric CV% will also be presented. For categorical data, frequency count and percentages will be presented. Data listings will be provided for all participants up to the point of withdrawal, with any participants excluded from the relevant population highlighted. Summary statistics and statistical analysis population. For the calculation of summary statistics and statistical analysis, unrounded data will be used.

Mean change from baseline is the mean of all individual participants' change from baseline values. Each individual change from baseline will be calculated by subtracting the individual participant's baseline value from the value at the timepoint. The individual participant's change from baseline values will be used to calculate the mean change from baseline using a SAS procedure such as Proc Univariate.

Data analysis will be performed using SAS[®] Version 9.4 or greater.

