9.3.2 Pharmacokinetic Statistical Methodology

The modified full analysis population will be used for these analyses. The PK parameters for the MMTT and during exercise will be analyzed separately.

During the MMTT

Log-transformed PK parameters AUCs, and C_{max} from insulin lispro during the MMTT will be statistically analyzed using a mixed-effect model. The model will include treatment (Lyumjev or

Humalog) and period as fixed effects, and participant as a random effect. The least squares (LS) means will be back-transformed to produce the treatment geometric LS means, ratio of geometric LS means of Lyumjev to Humalog, and corresponding 90% CIs, as well as the p-value, will be reported.

Example of the SAS code is as follows:

```
proc mixed data=xxx;
  class treat period usubjid;
  model logPK = treat period /residual ddfm=kr;
  random usubjid;
  lsmeans treat / cl pdiff alpha=0.1;
  estimate `Lyumjev vs Humalog' treat 1 -1/ CL alpha=0.1;
  ods output lsmeans=lsm diffs=estims;
run;
```

The same analysis without log transformation will be performed on the PK time parameters (early 50% t_{max} , late 50% t_{max} , and t_{max}) during the MMTT. The treatment LS means, treatment difference in LS means between Lyumjev and Humalog, and corresponding 90% CIs, as well as the 2-sided p-value, will be reported. The treatment ratios and 90% CIs for the ratios will be calculated using the Fieller's theorem³, see Appendix 2 for further details on this calculation.

Statistical significance will be achieved when the p-value for a test is less than 0.10.

During exercise

A mixed-effects model without log transformation that includes treatment (Lyumjev with 50% basal reduction, Lyumjev with 100% basal reduction, Humalog with 50% basal reduction, and Humalog with 100% basal reduction), sequence, and period as fixed effects and participant-within-sequence as a random effect may be used for the exploratory PK endpoints during the exercise period. LS means, treatment differences in LS means, and the corresponding 90% CIs for the treatment differences will be estimated from the model. The p-value on the difference between LS means will be used to determine statistical significance. The treatment ratios and 90% CIs for the ratios will be calculated using the Fieller's theorem (Chow and Liu 2009).

Additionally, exploratory analysis may be conducted if deemed necessary upon review of the data.

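### Exercise-period lispro AUC is modelled untransformed although the SAP calls PK AUCs log-normal; this costs power at 100% basal reduction, by an amount that depends on an exposure ratio the documents do not give

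*SAP*

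**What the plan says.** SAP 9.1 prescribes geometric summaries "for log-normal data (e.g. the PK parameters: AUCs and maximum observed drug concentration" (Cmax). SAP 9.3.2 applies this to the meal test: log-transformed lispro AUCs and Cmax "from insulin lispro during the MMTT will be statistically analyzed using a mixed-effect model", with back-transformed ratios and 90% CIs. There the untransformed scale is kept for time parameters only.

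Under the exercise heading of the same section the plan changes scale: "A mixed-effects model without log transformation that includes treatment" at four levels (two products by two basal reductions), plus sequence and period, with participant-within-sequence as the random effect. It reports differences, 90% CIs and Fieller ratios. Protocol 9.3.3.2.2 is also untransformed, though it names only the two products: "A mixed-effects model without log transformation that includes treatment (Lyumjev, Humalog), sequence, period, and treatment as fixed effects". Neither document explains the change.

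SAP 9.3.1 lists three parameters for the basal suspension period: terminal half-life, tlast and AUC(0-tlast), the last counted from the time of suspension.

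On status, SAP 4.2 lists "Insulin lispro PK during the exercise" as a secondary endpoint. SAP 9.3.2 says its model "may be used for the exploratory PK endpoints during the exercise" period.

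**The concern.** If AUC is log-normal, a product effect is roughly constant as a ratio, and its spread in absolute units grows with the level. Two things follow on the raw scale. Participants with high exposure dominate the mean difference, which costs power even when both reductions give the same exposure. And if exposure is higher at 50% than at 100% reduction, one residual variance averages over unequal spreads: too large for B versus D (Lyumjev versus Humalog at 100%), possibly too small for A versus C (at 50%).

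Exercise PK is the secondary comparison that would help to explain a glucose difference under basal reduction. An insensitive or mis-sized interval, or an analysis that may be left out, weakens that explanation.

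**Working it through.** **Plan's own figure.** The documents give no power for exercise PK. The only sample-size statement concerns the primary glucose endpoint: "Approximately 32 participants may be enrolled to ensure that at least 28 participants complete the study", for "approximately 80% power to demonstrate a 14-mg/dL difference" with SD 27.9 mg/dL and two-sided alpha 0.10. Reading 27.9 as the SD of the within-participant difference, a paired t-test needs 26 participants for 80% power and has 82.7% at 28. So 28 completers is consistent, and it is used below.

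**Inputs from the documents.** 28 participants; the four sequences in SAP 6; a four-level treatment effect (SAP 9.3.2); log-normal AUC (SAP 9.1). Residual df = 112 − 28 − 3 − 3 = 78.

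**Assumptions not in the documents.** r = AUC at 50% / AUC at 100%; between-participant log SD σ_b; within-participant log SD σ_w, where σ_w² = ln(1 + CV²). One guide to σ_b: a log-uniform spread over the eligible total daily dose (0.25 to 1.2 U/kg, protocol 5.1) has log SD ln(4.8)/√12 = 0.45.

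**Step 1: interval width.** Set mean AUC to 1 at 100% and r at 50%. The variance that matters for a product contrast at level m is

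v_m = m² · exp(2σ_b²) · exp(σ_w²) · (exp(σ_w²) − 1).

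The single residual mean square averages the two product contrasts and the 50%-versus-100% contrast. The last also carries (r − 1)² exp(σ_w²) exp(σ_b²)(exp(σ_b²) − 1), because participants differ in absolute drop. Hence, relative to a correctly sized interval,

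width at 100% ≈ √{ (r² + 1)/2 + (r − 1)²(exp(σ_b²) − 1) / [3 exp(σ_b²)(exp(σ_w²) − 1)] },

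and width at 50% is that value divided by r.

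| r, σ_b, σ_w | Expression under the root | 100%: formula (simulated) | 50%: formula (simulated) |
|---|---|---|---|
| 1.12, 0.3, 0.3 | 1.127 + 0.004 | 1.06 (1.06) | 0.95 (0.95) |
| 2.0, 0.3, 0.3 | 2.5 + 0.305 | 1.67 (1.65) | 0.84 (0.83) |
| 2.0, 0.5, 0.2 | 2.5 + 1.807 | 2.08 (2.01) | 1.04 (1.02) |

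Over σ_b 0.2–0.5 and σ_w 0.2–0.3, simulated coverage of the nominal 90% interval was:

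| r | 100% reduction | 50% reduction |
|---|---|---|
| 1.05–1.12 | 0.91–0.92 | 0.88–0.90 |
| 1.48 | 0.96–0.98 | 0.84–0.89 |
| 1.74–2.25 | 0.98–0.999 | 0.81–0.92 |

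Log-scale coverage was 0.895–0.906 throughout. An untransformed analysis with a separate variance per reduction level also held about 0.90.

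**Step 2: power, B versus D.** True Lyumjev/Humalog ratio 0.85, σ_b 0.25–0.60, CV 20–40%, two-sided 0.10:

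| r | Untransformed | Log scale |
|---|---|---|
| 1.0 | 37–91% | 46–92% |
| 1.25 | 27–86% | 45–92% |
| 1.5 | 20–75% | 47–92% |
| 2.0 | 7–51% | 46–93% |

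Setting by setting, the loss is 1–10 points at r = 1.0 and 34–76 points at r = 2.0. With no product difference, the nominal 10% test of B versus D rejects about 10% of the time at r = 1.0, 2–4% at r = 1.5, and 1% or less at r = 2.0. For A versus C it rejects 9–12% at r = 1.0–1.1 and 7–18% at r = 1.5–2.0.

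**Step 3: what r might be.** Assume first-order decline from basal steady state and ignore the lunch bolus. SAP 5 gives the start times: 60 minutes before exercise for 50%, 15 minutes for 100%. With an assumed half-life of 60 minutes, k = ln 2/60 = 0.01155 per minute:

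- Exercise hour only. 50%: start level 0.75, AUC = 30 + 0.25 × 0.5/k = 40.8. 100%: start level 0.841, AUC = 0.841 × 0.5/k = 36.4. r = 1.12.
- From reduction to end of exercise. 50% (120 min): 60 + 0.5 × 0.75/k = 92.5. 100% (75 min): (1 − 0.420)/k = 50.2. r = 1.84.

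Half-lives of 30 to 90 minutes give r = 1.05–1.48 for the first window and 1.74–2.25 for the second. The AUC window therefore decides much of the effect.

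**The case against.** A reader might infer that the 100% interval is always far too wide, that its contrast loses most of its power, and that the 50% contrast always has an inflated error rate. The documents do not support that. They give no r, and the staggered start times pull the exposures together during the exercise hour: at r = 1.05–1.12 the 100% interval is only about 1–6% too wide. At 50% reduction the error rate is not inflated when between-participant spread is large and within-participant CV small.

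Other objections also have weight:

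- The common residual variance is inferred from silence; the only sample code is for the meal test.
- The exercise sentence names no parameter. Two of the three in SAP 9.3.1 are time parameters, for which the raw scale is reasonable. AUC(0-tlast) runs from suspension, so its use in the 50% arms is unclear.
- The 0.45 guide for σ_b comes from total daily dose, not basal rate, and enrolment is narrower than that range suggests. For this reason the power grid starts at 0.25.
- SAP 9.3.1 leaves open baseline subtraction during basal reduction. With falling insulin this can give zero or negative AUCs, so logs alone are not a complete fix.
- The SAP already asks for geometric summaries and Fieller ratios. But the Fieller ratio is built on arithmetic LS means, and the p-value that decides significance stays on the raw scale.

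These points limit the size of the effect and shape the remedy. They do not explain the change of scale, and they leave the secondary-versus-exploratory conflict untouched.

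**Conclusion.** The point holds in conditional form. The inconsistency of scale is in the text of both documents. Given the SAP's own premise of log-normal AUC, power at 100% reduction was lower untransformed in every setting examined: slightly at r = 1.0, severely at r = 2.0. The mis-sized intervals need r above 1 and the default single residual variance; undercoverage at 50% also depends on the spreads. The stronger unconditional reading is not established, since r, the spreads and the AUC window are all assumptions here.

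The conflict over status needs no simulation: a listed secondary endpoint is called exploratory and its model is optional. The primary endpoint and the sample size are not affected. The change should be made, but it does not threaten the trial's main conclusion.

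**What to change.** In SAP 9.3.2 (exercise) and protocol 9.3.3.2.2:

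1. Analyse exercise-period lispro AUCs without baseline subtraction on the log scale. Report geometric LS means and the Lyumjev/Humalog ratio with 90% CI within each basal reduction.
2. If a baseline-subtracted AUC is used and non-positive values occur, fall back to the untransformed analysis, as SAP 9.4.2 does for glucose AUCs, with a separate residual variance per basal-reduction level.
3. Keep the untransformed model for time parameters.
4. State whether AUC(0-tlast) applies to the 50% arms, and from what start time.
5. Replace "may be used for the exploratory PK endpoints during the exercise" with wording that the model will be used for the secondary PK endpoints during exercise.

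The cost is wording in the two documents and a small change of model code. No new data are needed.

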9.4 Pharmacodynamic Assessment

9.4.1 Pharmacodynamic Analysis

Blood Ketones and Free Fatty Acids

Blood ketones and free fatty acids data will be summarized by timepoint and treatment, and listed.

Glucodynamic Parameter Estimation

Glucodynamic data will be determined from the plasma glucose (PG) reported from the YSI glucose analyzer during the exercise and MMTT assessment.

Glucodynamic data will be analyzed for the participants during each exercise and MMTT assessment. During the exercise period, the change from baseline value (the 0-hour time point prior to the start of exercise) for each participant will be calculated to derive the change in PG level from start to end of exercise.

The rate of PG during the exercise, the nadir PG, decremental AUC, for each exercise assessments will be calculated.

During the MMTT, the change from baseline values CCI

for each participant will be calculated. The approach used will be documented in the CSR.

The area under the baseline subtracted PG concentration versus time curve (incremental) (iAUC) will be calculated during the MMTT for each in-house periods; the list of derived iAUCs are:

- The incremental AUC from time zero to 30 minutes postmeal (iAUC0-30min)
- The incremental AUC from time zero to 1-hour postmeal (iAUC0-1hour)
- The incremental AUC from time zero to 2-hours postmeal (iAUC0-2hour)
- The incremental AUC from time zero to 3-hours postmeal (iAUC0-3hour)
- The incremental AUC from time zero to 4-hours postmeal (iAUC0-4hour)

In addition, the change from baseline maximum PG observed during the 4 hours postmeal $(\Delta PGmax)$ and change from baseline 1-hour plasma glucose $(\Delta PG1h)$ and 2-hour plasma glucose after the start of the meal $(\Delta PG2h)$ will be calculated. Other partial iAUCs may be calculated, as deemed appropriate.

The mean data will be presented by summary statistics and presented by treatment for those participants who received both treatments (Lyumjev and Humalog) with the same insulin dose (bolus dose for the MMTT or basal reduction) and meal consumption. The data will also be listed.

This will be the responsibility of Eli Lilly and Company.

9.4.2 Pharmacodynamic Statistical Methodology

Primary glucodynamic endpoint

Changes in PG from the start to end of exercise will be statistically analyzed using a mixed– effect model. The model will include treatment (Lyumjev with 50% basal reduction, Lyumjev with 100% basal reduction, Humalog with 50% basal reduction, and Humalog with 100% basal reduction), sequence, period, timepoint, treatment-by-timepoint interaction as fixed effects, and participant-within-sequence as a random effect. Baseline (0 min timepoint) will be included as a covariate. The LS means, difference LS means between Lyumjev and Humalog for corresponding basal rate reduction, and corresponding 90% CIs, as well as the p-value, will be reported.

The p-value on the difference between LS means will be used to determine statistical significance.

Secondary glucodynamic endpoints

For the derived glucodynamic parameters iAUCs Δ PGmax, Δ PG1h, and Δ PG2h, a statistical analysis will be performed during exercise with a basal reduction, and after the MMTT independently. The modified full analysis population will be used for this analysis.

The parameters iAUCs during the MMTT and AUCs during exercise will be log-transformed before the statistical analysis. If negative values occur, the analysis will be performed on untransformed parameters. A mixed effects model will be used for this analysis. The model will include treatment (Lyumjev with 50% basal reduction, Lyumjev with 100% basal reduction, Humalog with 50% basal reduction, and Humalog with 100% basal reduction), sequence, and period as fixed effects, and participant-within-sequence will be included as a random effect. The LS means will be back-transformed to produce geometric means. The treatment geometric LS mean of each treatment, ratio of geometric means between Lyumjev and Humalog for corresponding basal rate reduction, and corresponding 90% CIs will be reported. The p-value will also be reported for the ratios. If the analysis is done on the untransformed parameters, the treatment LS means, difference in LS means between Lyumjev and Humalog for corresponding

basal rate reduction, and corresponding 90% CIs, as well as the p-value, will instead be reported. The treatment ratios and 90% CIs for the ratios will be calculated using the Fieller's theorem.

The rate of change in PG during exercise period and exploratory GD time parameters will also be statistically analyzed. A mixed effect model will be used, identical to the one above, on the actual values of the parameters. The LS means, difference in LS means between Lyumjev and Humalog for corresponding basal rate reduction, and corresponding 90% CIs, as well as the p-value, will be reported. The treatment ratios and 90% CIs will be reported using Fieller's theorem.

Additionally, exploratory analysis may be conducted if deemed necessary upon review of the data.

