lispro, glucose, FFA, and ketones sampling prior to lunch. The insulin dose for these
standardized meals (dinner, breakfast, and lunch) before exercise will be individualized per
participant to cover the carbohydrate content (including any correction bolus) and will be
administered immediately prior (0 to 2 minutes) to the meal using a $\mathbf{CC}$
No additional bolus insulin injection should be administered
post-meal after lunch prior to the exercise period. The basal rate will be set to a single hourly rate
at lunch CC based on the participant's usual basal rate for this time of day;
this will be maintained until the basal reduction for the exercise period. A pre-exercise glucose
target level of CC mg/dL will need to be achieved minutes prior to exercise. If glucose
level is below $\overline{90 \text{ mg/dL}}$ , ~16 g of oral carbohydrates will be administered. CC

prior to exercise, the

period will be rescheduled as mentioned in Section 5.2.1.

Based on the randomization, the pump basal rate will be reduced either 60 minutes or 15 minutes prior to the start of exercise period, scheduled for approximately **CCI** in the following manner:

- 50% basal insulin reduction 60 minutes prior to exercise until end of exercise
- 100% basal insulin reduction 15 minutes prior to exercise until end of exercise CCI

Participants will begin the exercise assessment at approximately 4 hours after lunch **CCI** They will be instructed to walk or light jog on the treadmill at approximately 45% to 55% of their predetermined peak VO2 using three 17-minute intervals with two 4-minute and 30-second rest periods in between the intervals for 1 hour. During this period, samples will be collected for glucose, insulin lispro, ketones and FFAs per the SoA (Section 1.3). Heart rate will be monitored, and participants will be asked to rate their perceived exertion using 6-20 Borg RPE scale (Section 8.2.8) during the last 2 minutes of each 17-minute interval, as per the assessment day visit. If hypoglycemia ensues (plasma or whole blood glucose level **CCI** the exercise will be terminated, and the participant will be treated with **CCI** of oral carbohydrates. If the glucose level continues to be below **CCI** after approximately minutes, up to an additional **CCI** of oral carbohydrates can be provided. Repeat as necessary if glucose value remains below **CCI**/dL.

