#### 9.3.2.2.1. Statistical Analysis of the Primary Endpoint Change in Plasma Glucose during Exercise

Changes in plasma glucose will be compared between Lyumjev versus Humalog from the start to the end of exercise during either 50% or 100% reduction of basal infusion rates.

For the primary endpoint, the change in plasma glucose will be analyzed using a mixed-effect model that includes treatment (Lyumjev, Humalog), sequence, period, and treatment as fixed effects and participant within sequence as a random effect. LSmeans, treatment differences in LSmeans, and the corresponding 90% CIs for the treatment differences will be estimated from the model. The p-value on the difference between LSmeans will be used to determine statistical significance.

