4. STUDY OBJECTIVES AND ENDPOINTS

4.1 **Primary Objective and Endpoint**

The primary objective of the study is:

• To compare changes in plasma glucose (PG) levels with LyumjevTM versus Humalog[®] from the start to the end of 60 minutes of moderate-intensity aerobic exercise using either 50% or 100% reduction of basal infusion rates, set 60 minutes or 15 minutes before the onset of exercise, respectively.

The primary endpoint of the study is:

• Changes in PG from the start to the end of exercise.

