11. CHANGES FROM THE PROTOCOL SPECIFIED STATISTICAL ANALYSES

There were no changes from the protocol specified statistical analyses.

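### The primary model uses several glucose samples per exercise session but states no within-session covariance and names no end-of-exercise contrast

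*SAP*

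**What the plan says.** SAP Section 4.1 gives the primary endpoint as "Changes in PG from the start to the end of exercise". Under SAP Section 9.4.1 the difference from the 0-hour value "will be calculated to derive the change in PG level from start to end of exercise". That is one value per participant per period.

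SAP Section 9.4.2 then models this endpoint with a four-level treatment factor (each insulin at each basal reduction), "sequence, period, timepoint, treatment-by-timepoint interaction as fixed effects, and participant-within-sequence as a random effect", and the 0-minute glucose as covariate. A timepoint term makes sense only with several records per session. The section gives no participant-by-period effect, residual covariance or degrees-of-freedom method for this model. What is reported is "The LS means, difference LS means between Lyumjev and Humalog for corresponding basal rate reduction", with 90% CIs and a p-value; no timepoint is named. Nothing is marked as redacted in that paragraph.

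The only SAS code in the SAP (Section 9.3.2, meal-test PK) has "random usubjid", LS means by treatment, and no REPEATED statement.

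Protocol Section 9.3.2.2.1 has a different model: "the change in plasma glucose will be analyzed using a mixed-effect model that includes treatment (Lyumjev, Humalog), sequence, period, and treatment as fixed effects". It contains no timepoint, interaction or baseline term. SAP Section 11 nevertheless says: "There were no changes from the protocol specified statistical analyses".

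**The concern.** Samples from one exercise session share that session's deviation: the same day, the same infusion site, the same starting state. A participant intercept captures only what is common to all four of a participant's sessions. If nothing else is specified, the session deviation is treated as independent noise in every sample. The end-of-exercise variance is also replaced by a variance pooled over all modelled timepoints. For a change from a 0-minute baseline, spread naturally grows with time, so the pooled figure is likely to be too low at the end.

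The second problem is the target. With timepoint in the model, treatment LS means average over the modelled samples unless a timepoint is named. That average is not the start-to-end change. Two analysts following the same text could report different primary contrasts.

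The p-value and 90% CI from this model decide the primary comparison, at a two-sided 0.10 level and without multiplicity adjustment (Protocol Section 9.1.1). Sessions can also stop early: on hypoglycemia, "the exercise will be terminated, and the participant will be treated with" oral carbohydrate. The plan does not say which value is then the end value.

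**Working it through.** **Inputs.** From SAP Section 7: 28 completers, difference 14 mg/dL, SD 27.9 mg/dL, two-sided alpha 0.10, about 80% power. From SAP Section 6: sequences A/D/B/C, B/A/C/D, C/B/D/A, D/C/A/B. Assumed: 2 to 6 equally spaced post-baseline samples ending at 60 minutes (the real times are redacted), the within-session covariance, and the between-participant SD of the change.

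**The plan's own figure.** SAP Section 7 does not say what kind of SD 27.9 is. Read as the SD of the paired difference, n = (27.9 × (1.645 + 0.842) / 14)² = 24.6, so 25. A paired t calculation gives 26, and rounding up to a multiple of four sequences gives 28. Power at 28 is 82.7% (t) or 84.4% (z). If 27.9 were a per-session SD with uncorrelated sessions, power would be 57%. The paired reading fits the stated N, so it sets the scale: per-session SD 27.9/√2 = 19.7, and true SE of one contrast 27.9/√28 = 5.27 mg/dL.

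**Why the listed model goes wrong.** Let v be the per-session variance, ρ the within-session correlation and T the number of samples, with constant variance. The residual variance that a participant intercept leaves is about v[(1 − ρ) + 3Tρ/(4T − 1)]. For T = 3 and ρ = 0.5 this is v(0.5 + 0.409) = 0.909v.

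- End contrast: model SE / true SE ≈ √0.909 = 0.95 (simulated 0.94).
- Time-averaged contrast: the model uses 0.909v/3 = 0.303v; the truth is v(0.5 + 0.5/3) = 0.667v; ratio √(0.303/0.667) = 0.67 (simulated 0.66).

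If variance grows as a random walk with T = 3, the pooled variance is (1/3 + 2/3 + 1)/3 = 2/3 of the end variance. That alone gives √(2/3) = 0.82; the simulated ratio is 0.77.

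**Null simulations of the listed model.** Settings: 7 participants per sequence, 0-minute covariate, REML random intercept, independent residuals, residual degrees of freedom, and 1,000 or 2,000 trials per cell. Nominal type I error is 10%.

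| Assumed within-session pattern | End contrast | Time-averaged LS means |
|---|---|---|
| Variance grows, participant SD 0–20 mg/dL | 16–31% | 15–48% (all participant SDs) |
| Variance grows, participant SD 40 mg/dL | 10–15% | as above |
| Constant variance, ρ = 0.5–0.8 | 11–15% | 18–50% |
| Variance grows; values held once below an assumed 70 mg/dL | 19–25% | 22–45% |
| Independent samples | 10–11% | 10–11% |
| One value per session, all patterns | 8–12% | not applicable |

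For the end contrast, model SE / true SE is 0.62–0.99 with growing variance and 0.90–0.98 with constant variance. With 3 samples and session-specific slopes the SEs are 3.8 and 5.4 mg/dL.

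A separately coded simulation (participant SD 10; 3, 4 or 6 samples; 1,500 trials) agrees. Its end-contrast type I error is 20–30% with growing variance and 12–15% with constant variance and correlation. It is 9–10% with independent samples, and also when variance falls toward the end with correlation 0.5. One value per session gave SE 5.28 against an empirical 5.28, and type I error 9.6% (8,000 trials).

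**Target.** If a true 14 mg/dL end difference builds up linearly, the time-averaged difference is 14 × (T + 1)/(2T): 9.3, 8.75 and 8.2 mg/dL for T = 3, 4 and 6.

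**The case against.** The strongest reply is that silence is not a choice. Section 9.4.2 lists terms in prose and never says residuals are independent, and the only code is for a PK model with one value per period, where no REPEATED statement is needed. A team could add a covariance structure, and the error need not then be in the same direction. With 3 samples, an unstructured within-session covariance plus a participant intercept gave type I error of 1.7–3.3% under growing variance, with SE 7.1–7.5 against a true 5.1–5.3: too wide. A treatment-by-timepoint term is also normally included to compare treatments at given times, so an analyst might well choose the end of exercise.

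Part of this stands. The size cannot be fixed from the documents, and the end-contrast results include cases with no inflation. The largest rates belong to the time-averaged contrast, which the SAP does not explicitly request. Holding values after an early stop is an assumption, not an SAP rule. A repeated model can also use partial sessions, whereas one value per session needs a rule for them. SAP Section 3 says the SAP supersedes the protocol's statistical section, and the document history logs an update to the primary analysis in version 2.0.

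It does not remove the problem. The terms that are listed give wrong error bars when samples within a session are correlated, except in special cases. That other completions err the other way shows that the covariance must be prespecified. SAP Section 3 also promises to identify substantial differences from the protocol, and Section 11 denies any.

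**Conclusion.** The concern holds and must be fixed, because it affects the primary p-value and interval. Fitted as listed, the model generally understates the standard error. For an end-of-exercise contrast at nominal 10%, type I error is about 16–31% if variance grows over exercise and participant SD is 0–20 mg/dL, 10–15% if that SD is 40, and 11–15% with constant variance and correlated samples. There is essentially no inflation if samples within a session are independent, or in the case tested where variance falls toward the end. If default treatment LS means are reported, the estimate is a time average and does not match the endpoint.

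These sizes rest on assumed sampling times and covariances, and on reading 27.9 mg/dL as a paired SD. Four textual points need no simulation: participant is the only random effect, no within-session covariance is stated, no timepoint is named, and Section 11 contradicts the change from the protocol model.

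**What to change.** - Analyse one end-of-exercise change per participant-period. Fixed terms: four-level treatment, sequence, period and 0-minute glucose. Random term: participant-within-sequence. Use Kenward-Roger degrees of freedom.
- Name A minus C (50% reduction) and B minus D (100% reduction) at the end of exercise as the primary contrasts.
- State which glucose value is analysed when a session ends early.
- Record the departure from the protocol model in SAP Section 11.

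If timepoints are kept, specify covariance over timepoints at both the participant and the participant-by-period level, and name the end-of-exercise contrast. In simulation with 3 samples this gave type I error of 8.4% (251 trials) and 10.9% (327 trials); the small trial counts make these figures rough.

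The cost is SAP wording and a few lines of SAS, plus the decision on early-stopped sessions. The interval will usually be wider, because it then reflects the actual uncertainty.
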